The CBCL is a widely used method of identifying problem behavior in children.^{1,2} It is a component in the ASEBA. It is a detailed, specific measure of competencies, adaptive functioning, and behavioral/emotional problems in children, split into competencies and problems. The CBCL has been shown to have good reliability and validity,² and has been used in many pediatric populations with different disorders, including epilepsy.^{5,13,34}

Problems are identified by a respondent who knows the child well, usually a parent. There are two versions of the CBCL-Parent version. The preschool checklist (CBCL/1½-5) is intended for use with children 18 months to 5 years of age (see [Attachment 6](#) for an example). The school-age version (CBCL/6-18) is for children 6 to 18 years of age (see [Attachment 7](#) for an example).

The checklists consist of a number of statements about the child's behavior, eg, "Acts too young for his/her age." Responses are recorded on a Likert scale: 0=not true, 1=somewhat or sometimes true, 2=very true or often true. The preschool checklist contains 99 questions and the school-age checklist contains 112 questions.

Similar questions are grouped into a number of syndromes, eg, Aggressive behavior, and their scores are summed to produce a score for that syndrome. Some syndromes are further summed to provide scores for Internalizing (Anxious/Depressed, Withdrawn/Depressed, and Somatic Complaints) and Externalizing problem scales (Rule-Breaking Behavior and Aggressive Behavior). A total score from all questions is also derived. For each syndrome, problem scale, and the total score, tables are given that determine whether the score represents normal, borderline, or clinical behavior. These categorizations are based on quantiles from a normative sample.

Suicidality

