0 1 2 1. Acts too young for his/her age 0 1 2 2. Drinks alcohol without parents' approval 0 1 2 3. Argues a lot 0 1 2 4. Fails to finish things he/she starts 0 1 2 5. There is very little he/she enjoys 0 1 2 6. Bowel movements outside toilet 0 1 2 7. Bragging, boasting 0 1 2 8. Can't concentrate, can't pay attention for long 0 1 2 9. Can't get his/her mind off certain thoughts; obsessions 0 1 2 10. Can't sit still, restless, or hyperactive 0 1 2 11. Clings to adults or too dependent 0 1 2 12. Complains of loneliness 0 1 2 13. Confused or seems to be in a fog 0 1 2 14. Cries a lot 0 1 2 15. Cruel to animals 0 1 2 16. Cruelty, bullying, or meanness to others 0 1 2 17. Daydreams or gets lost in his/her thoughts 0 1 2 18. Deliberately harms self or attempts suicide 0 1 2 19. Demands a lot of attention 0 1 2 20. Destroys his/her own things 0 1 2 21. Destroys things belonging to his/her family or others 0 1 2 22. Disobedient at home 0 1 2 23. Disobedient at school 0 1 2 24. Doesn't eat well 0 1 2 25. Doesn't get along with other kids 0 1 2 26. Doesn't seem to feel guilty after misbehaving 0 1 2 27. Easily jealous 0 1 2 28. Breaks rules at home, school, or elsewhere 0 1 2 29. Fears certain animals, situations, or places, other than school 0 1 2 30. Fears going to school 0 1 2 31. Fears he/she might think or do something bad	0 1 2 32. Feels he/she has to be perfect 0 1 2 33. Feels or complains that no one loves him/her 0 1 2 34. Feels others are out to get him/her 0 1 2 35. Feels worthless or inferior 0 1 2 36. Gets hurt a lot, accident-prone 0 1 2 37. Gets in many fights 0 1 2 38. Gets teased a lot 0 1 2 39. Hangs around with others who get in trouble 0 1 2 40. Hears sound or voices that aren't there 0 1 2 41. Impulsive or acts without thinking 0 1 2 42. Would rather be alone than with others 0 1 2 43. Lying or cheating 0 1 2 44. Bites fingernails 0 1 2 45. Nervous, highstrung, or tense 0 1 2 46. Nervous movements or twitching 0 1 2 47. Nightmares 0 1 2 48. Not liked by other kids 0 1 2 49. Constipated, doesn't move bowels 0 1 2 50. Too fearful or anxious 0 1 2 51. Feels dizzy or lightheaded 0 1 2 52. Feels too guilty 0 1 2 53. Overeating 0 1 2 54. Overtired without good reason 0 1 2 55. Overweight 0 1 2 56. Physical problems without known medical cause: 0 1 2 a. Aches or pains (not stomach or headaches) 0 1 2 b. Headaches 0 1 2 c. Nausea, feels sick 0 1 2 d. Problems with eyes (not if corrected by glasses) 0 1 2 e. Rashes or other skin problems 0 1 2 f. Stomachaches 0 1 2 g. Vomiting, throwing up			

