Be sure you answered all items. Then see other side.				

Please print. Be sure to answer all items.

0 = Not True (as far as you know)	1 = Somewhat or Sometimes True	2 = Very True or Often True
0 1 2 57. Physically attacks people	0 1 2 84. Strange behavior	
0 1 2 58. Picks nose, skin, or other parts of body	0 1 2 85. Strange ideas	
0 1 2 59. Plays with own sex parts in public	0 1 2 86. Stubborn, sullen, or irritable	
0 1 2 60. Plays with own sex parts too much	0 1 2 87. Sudden changes in mood or feelings	
0 1 2 61. Poor school work	0 1 2 88. Sulks a lot	
0 1 2 62. Poorly coordinated or clumsy	0 1 2 89. Suspicious	
0 1 2 63. Prefers being with older kids	0 1 2 90. Swearing or obscene language	
0 1 2 64. Prefers being with younger kids	0 1 2 91. Talks about killing self	
0 1 2 65. Refuses to talk	0 1 2 92. Talks or walks in sleep	
0 1 2 66. Repeats certain acts over and over; compulsions	0 1 2 93. Talks too much	
0 1 2 67. Runs away from home	0 1 2 94. Teases a lot	
0 1 2 68. Screams a lot	0 1 2 95. Temper tantrums or hot temper	
0 1 2 69. Secretive, keeps things to self	0 1 2 96. Thinks about sex too much	
0 1 2 70. Sees things that aren't there	0 1 2 97. Threatens people	
0 1 2 71. Self-conscious or easily embarrassed	0 1 2 98. Thumb-sucking	
0 1 2 72. Sets fires	0 1 2 99. Smokes, chews, or sniffs tobacco	
0 1 2 73. Sexual problems	0 1 2 100. Trouble sleeping	
0 1 2 74. Showing off or clowning	0 1 2 101. Truancy, skips school	
0 1 2 75. Too shy or timid	0 1 2 102. Underactive, slow moving, or lacks energy	
0 1 2 76. Sleeps less than most kids	0 1 2 103. Unhappy, sad, or depressed	
0 1 2 77. Sleeps more than most kids during day and/or night	0 1 2 104. Unusually loud	
0 1 2 78. Inattentive or easily distracted	0 1 2 105. Uses drugs for nonmedical purposes (don't include alcohol or tobacco)	
0 1 2 79. Speech problem	0 1 2 106. Vandalism	
0 1 2 80. Stares blankly	0 1 2 107. Wets self during the day	
0 1 2 81. Steals at home	0 1 2 108. Wets the bed	
0 1 2 82. Steals outside the home	0 1 2 109. Whining	
0 1 2 83. Stores up too many things he/she doesn't need	0 1 2 110. Wishes to be of opposite sex	
	0 1 2 111. Withdrawn, doesn't get involved with others	
	0 1 2 112. Worries	

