The Vineland Scales of Adaptive Behavior provide age-specific assessment of function in the domains of communication, daily living, socialization, and motor skills, as well as a composite scale. The subject's sub-domain raw scores are entered on the CRF. The derived domain scores (standardized scores) based on the national standardization sample must be obtained from these raw scores. The derived scores are used in the analyses. The Vineland standardized scores for domain scores have a mean of 100 and a standard deviation of 15.

The composite score will be the sum of 4 standardized domain scores. If a subject has only 3 domains, then the standardized score for the missing domain will be prorated and the composite score will be calculated as sum of 4 domains. If a subject has less than 3 domains, then the composite score will not be calculated.

The standardized scores and the changes in standardized scores from baseline will be listed and summarized by visit using descriptive statistics.

For manuals and SAS program calculating the standardized domain scores, please see [Appendix 4](#).

The Vineland Adaptive Behavior Scale will be administered for subjects 2 to 5 years of age only.

Behavioral Assessments

For CBCL preschool (up to 5 years of age), a raw total score will be sum of 99 non-missing answers (range of 0-198).

For CBCL school age (6 to 18 years of age), a raw total score will be the sum of 112 non-missing answers (range of 0-224).

The domains will be:

CBCL preschool	CBCL school age
1. Emotionally Reactive	11. Anxious/depressed
2. Anxious/Depressed	12. Withdrawn/depressed
3. Somatic Complaints	13. Somatic complaints
4. Withdrawn	14. Social problems
5. Sleep Problems	15. Thought problems
6. Attention Problems	16. Attention problems
7. Aggressive Behavior	17. Rule breaking behavior
8. Internalizing Problems	18. Aggressive behavior
9. Externalizing Problems	19. Internalizing Problems
10. Total Problems	20. Externalizing Problems
	21. Total Problems

The standardized total scores (T score) for all domains will be derived using the charts based on the raw scores ([Appendix 5](#)).

The standardized scores and the changes in standardized scores from baseline will be listed and summarized by visit using descriptive statistics.

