If a teacher checked two boxes for one subject, use the mean of the two scores assigned to these boxes.

Enter the *mean* of the teacher's ratings for all academic subjects beneath the heading *Academic Performance* on the profile. (Academic subjects include reading, writing, arithmetic, spelling, science, English, foreign language, history, social studies, computer programming, etc. Do *not* count physical education, art, music, home economics, driver education, industrial arts, typing, or the like.)

Item VIII. For each of the questions 1-4, score the teacher's ratings as follows:

Much less = 1
Somewhat less = 2
Slightly less = 3
About average = 4
Slightly more = 5
Somewhat more = 6
Much more = 7

Enter the score for each rating beneath the appropriate heading on the profile.

Sum of Items VIII. 1-4. Sum the scores for Items VIII. 1, 2, 3, and 4. Enter this sum beneath the appropriate heading on the profile. Do *not* compute this sum if any of the 4 items is missing.

Scoring the CBCL/6-18, YSR, and TRF Problem Scales

Do *not* score the problem scales if data are missing for more than 8 items, not counting open-ended items 56h and 113, or YSR socially desirable items 6, 15, 49, 59, 60, 73, 80, 88, 92, 98, 106, 107, 108, 109. If TRF items 56a-56g were left blank, score them 0.

TRANSFERRING PROBLEM ITEM SCORES TO THE PROFILES

Templates. Templates are available to aid in transferring data from the school-age forms to the profiles. Different templates are needed for the CBCL/6-18, YSR, and TRF. To transfer problem item scores onto the profile, place the Page 3 template on Page 3 of the form. For each problem item, the template indicates whether the item's score is to be entered on a syndrome scale or on the *OTHER PROBLEMS* list of the profile of empirically based syndromes. The template also indicates the DSM-oriented scale on which to score each item. Repeat using the Page 4 template on Page 4 of the form.

Item Scores. For each problem item, print the respondent's 0, 1, or 2 response in the appropriate space beside the item on the profile form. If the respondent circled two numbers for an item, print 1 beside the item on the profile form. Comments written by the respondent should be used in judging whether items deserve to be scored, with the following guidelines:

1. For each problem reported by the respondent, only the item that most specifically describes the problem should be scored. If the respondent's comments show that more than

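### The school-age CBCL total in SAP 7.8 (112 answers, 0-224) conflicts with the study form (118 rated answers, 0-236) and with the scoring rules in SAP Appendix 5

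*SAP*

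**What the plan says.** SAP 7.8 (Behavioral Assessments) states for the school-age form that "a raw total score will be the sum of 112 non-missing answers (range of 0-224"), and for the preschool form that "a raw total score will be sum of 99 non-missing answers (range of 0-198"). It then derives T scores for every domain, including Somatic complaints, Internalizing and Total Problems, from the Appendix 5 charts. The planned summaries are of these standardized scores and their changes from baseline. Section 7.8 gives no limit on missing CBCL items, although it does give a missing-domain rule for the Vineland composite.

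Protocol 9.3 says that "The preschool checklist contains 99 questions and the school-age checklist contains 112 questions", that each is rated "0=not true, 1=somewhat or sometimes true, 2=very true or often true", and that "A total score from all questions is also derived".

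The school-age form in Protocol Attachment 7 runs to "0 1 2 112. Worries". Its question 56 is a lead-in followed by seven parts, each with its own rating, for example "0 1 2 b. Headaches 0 1 2 c. Nausea, feels sick".

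SAP Appendix 5 tells the scorer not to "score the problem scales if data are missing for more than 8 items", leaving the open-ended items 56h and 113 out of that count. Its profile lists the question 56 parts in a syndrome column. It adds the three leftmost syndrome scales into Internalizing and carries that sum into the total.

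**The concern.** Section 7.8 gives an operative scoring rule, and it appears to take the number of numbered questions as the number of rated answers. A programmer who follows it literally could build a Total Problems raw score that is not the sum of its own components. That score would then be looked up in a chart meant for the Appendix 5 total, and the T score would come out too low for children with somatic complaints.

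The second conflict is over missing items. A sum of whatever answers are present, with no lower limit, gives a mostly blank form a low problem score. At a post-baseline visit this would look like improvement. Behaviour disturbance is listed as an adverse event of clinical interest for levetiracetam, so an error in that direction is unwelcome even in a descriptive table.

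**Working it through.** **Inputs.** Maximum rating per answer: 2 (Protocol 9.3). Stated counts: 112 and 99 (SAP 7.8 and Protocol 9.3). Form layout: items 1-55, 56a-g and 57-112 (Protocol Attachment 7). Missing limit: more than 8 items (SAP Appendix 5).

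**1. The plan's own figures.** Maximum = answers × 2.
- School-age: 112 × 2 = 224, as stated.
- Preschool: 99 × 2 = 198, as stated.

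Both ranges follow from their stated counts, so the question is whether the counts are right.

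**2. Rated answers on the school-age form.**
- Items 1-55: 55
- 56a-g: 7
- Items 57-112: 112 − 57 + 1 = 56
- Total: 55 + 7 + 56 = 118; maximum 118 × 2 = 236
- Shortfall of the stated figure: 118 − 112 = 6 answers; 236 − 224 = 12 points

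**3. Does 112 correspond to any version of the form?** With 56a-g left out and the heading unrated, 55 + 56 = 111 answers remain, with maximum 222. So 112 and 0-224 match neither including nor excluding the parts. They match counting question 56 once, by its number.

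**4. The question 56 heading.** The extracted text shows a 0-1-2 beside the heading, which may be a layout artefact. If the heading really is rated, the form has 119 answers (0-238) and the shortfall is 7 answers, or 14 points. In that case the form without a-g would have 111 + 1 = 112 answers, so step 3 depends on the heading being unrated. On either reading, the full form does not have 112 answers.

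**5. Missing answers.** Appendix 5 sums the 1s and 2s entered, so a blank adds nothing, exactly as in a plain sum. The two rules agree for up to 8 missing items and differ only above that. The total is lowered by (number missing) × (mean true score of those items). The documents give no item means. Assuming 0.1 to 1.0:

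| Missing | Lowering (points) | Appendix 5 |
|---|---|---|
| 8 | 0.8 to 8.0 | scored, same result |
| 9 | 0.9 to 9.0 | not scored |
| 30 | 3.0 to 30.0 | not scored |
| 59 (half the form) | 5.9 to 59.0 | not scored |

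**6. From raw score to T score.** Section 7.8 points to the Appendix 5 charts but does not say whether its own total or the Appendix 5 total goes into them. The raw-score gap cannot be converted to T-score units from the charts as they appear in the document.

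**The case against.** The best defence is that 7.8 contains a miscounted label and not a scoring error. It sends the reader to Appendix 5, which builds its own total with the question 56 parts included and already refuses to score a form with more than 8 missing items. If the programmers followed Appendix 5, the T scores are right. Only T scores are summarized, and no formal testing is planned. The phrase about non-missing answers could also be read as requiring all the answers to be present.

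Much of this stands, and it rules out three stronger readings that a reader might infer:

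- **That the plan drops 56a-g.** Nothing in either document says so. SAP 7.8 keeps Somatic complaints as a domain, and Protocol 9.3 takes the total from all questions.
- **That 14 points are lost.** That figure assumes all seven parts are removed, or that the heading is rated. Against the form as counted here, the shortfall is 12 points.
- **That incomplete forms in general are scored as healthier than the instrument intends.** Up to 8 blanks, Appendix 5 treats them the same way. A loss of 60 points for 30 blanks would need every blank item to have been a true 2.

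The defence does not remove the conflict. Section 7.8 states a count, a range and an unlimited sum that differ from the appendix it cites, and it does not say which governs. Requiring all 112 answers would also depart from Appendix 5, which tolerates up to 8 missing items.

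**Conclusion.** The point holds as an inconsistency between SAP 7.8 on one side and the study form and SAP Appendix 5 on the other. The stated count and range are short by 6 answers and 12 points, assuming that the question 56 heading is not itself rated. The missing-item conflict affects only forms with more than 8 blanks; the documents do not say how many such forms to expect.

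Whether any reported T score is wrong depends on which total was programmed. If Appendix 5 was followed, none is. If 7.8 was followed literally, Total Problems could be too low, and a largely blank form could receive a score. Importance is low: the CBCL is summarized descriptively and is not among the key safety endpoints in Protocol 11.4. The correction is still worth making because it costs little and removes a real ambiguity.

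**What to change.** In SAP 7.8, replace the school-age sentence with a definition that:

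- makes the total the Appendix 5 total over the 118 rated answers on the study form, names 56a-56g as included and gives the range 0-236, after checking the form to confirm that the question 56 heading is unrated;
- notes that 56h and 113, which appear on the Appendix 5 profile, are not on the study form;
- sets scale and total scores to missing when more than 8 items are missing, as in Appendix 5.

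The instructions in Appendix 5 are headed for the 6-18 form and its companion forms, so a missing-item rule for the preschool form should also be stated. The documents do not supply one.

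The cost is a few lines of SAP text, a check of the scoring program and, if it followed 7.8 literally, a minor change and a rerun of the CBCL tables. No new data are needed.

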7.9. Adverse Events

Adverse events are coded to System Organ Class (SOC) and preferred terms (PT) using the Medical Dictionary for Regulatory Activities (MedDRA) coding system, version 21.1 or higher. Treatment-emergent adverse events (TEAEs) are those AEs which start or worsen after receipt of the first study drug and before the end of the REACH. REACH is defined as follows: AEs with onset date within therapeutic reach (i.e. 3 days) or SAEs/deaths with onset date within 30 days, inclusive, after end of treatment. AE's with partial onset date will be handled as follows: a missing day should be set to first of month. If month is missing the missing month should be set to January.

Summaries of TEAEs will be provided as incidence tables (number of subjects experiencing an event) by treatment group within each age group and overall (age 2-15). For each TEAE, the percentage of subjects who experience at least 1 occurrence of the given event will be summarized. Tables will be sorted by decreasing frequency in incidence (the highest to lowest incidence) first within the SOC and then the PT. Treatment-emergent serious AEs (SAEs), TEAEs leading to discontinuation, TEAEs by severity, TEAEs by relationship and TEAEs of special interest will be summarized. Adverse events of special interest for topiramate include: effects on liver function; metabolic acidosis; effects on growth and maturation; vision abnormalities; oligohidrosis, hyperthermia and secondary rash; hyperammonemia and/or encephalopathy; kidney stones; neuropsychiatric and cognitive disorders; and suicidality. Adverse events of clinical interest for levetiracetam are as listed previously, notably somnolence, asthenia, and behavior disturbances

(especially hostility and nervousness). Please see [Appendix 3](#) for the MedDRA codes for these AE of clinical interest.

A listing of AEs will also be provided.

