During the double-blind phase of study TOPMAT-EPMN-106, mean BMI decreases were observed for approximately half of the pediatric subjects in the topiramate 50-/400-mg/day group and topiramate 400-/400-mg/day group, with most of the remaining subjects showing no change in BMI. Larger BMI decreases followed 400 mg/day topiramate than followed 50 mg/day. Based on CDC criteria, topiramate treatment rarely resulted in underweight BMI among pediatric subjects with normal BMI values at baseline. Mean BMI decreases (-1.3 kg/m²) were observed at 6 months among pediatric subjects whose dosage increased from 50 to 400 mg/day during this study's open-label extension.³⁹

Weight, height, and BMI Z-scores decreased from baseline to endpoint in pediatric subjects in monotherapy studies. These results indicate that, in general, children continue to grow while receiving topiramate monotherapy treatment, although at a rate slower than their normal healthy counterparts.³³

Vision Abnormalities (Acute Myopia and Secondary Angle-Closure Glaucoma)

A medical condition consisting of sudden worsening of vision and an elevation of fluid pressure in the eyes (secondary glaucoma) has been described in clinical studies and post-marketing reports in subjects taking topiramate, usually at the beginning of their treatment. In contrast to primary narrow-angle glaucoma, which is rare under 40 years of age, secondary angle-closure glaucoma associated with topiramate has been reported in pediatric as well as adult subjects. Symptoms include acute onset (within 1 month of initiating topiramate therapy) of decreased visual acuity and/or ocular pain. Ophthalmologic findings can include myopia, anterior chamber shallowing, ocular hyperemia (redness), and increased intraocular pressure. Mydriasis may or may not be present. The primary treatment to reverse symptoms is discontinuation of topiramate as rapidly as possible according to the judgment of the treating physician.³³

Visual field defects have been reported in subjects receiving topiramate independent of elevated intraocular pressure. In clinical studies, most of these events were reversible after topiramate discontinuation. If visual problems occur at any time during topiramate treatment, consideration should be given to discontinuing the drug.

Oligohidrosis, Hyperthermia, and Secondary Rash

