Only AED monotherapy will be used for both treatment groups. However, subjects will not be discontinued from the study if 1 or more concomitant AEDs are added after initiating treatment with study drug. Data will be collected prior to the use of the concomitant AED(s) for the primary analysis. Data subsequently collected while on the concomitant AED(s) will be analyzed in a secondary analysis for each safety outcome of interest.

All subjects will enter a 30-day posttreatment phase after completing the open-label treatment phase.

The open-label treatment phase has 2 periods, titration and maintenance.

Titration Period

Randomization will take place on Day 1 (Visit 2). The Day 1 visit will serve as the baseline visit. All procedures on Day 1 (except dispensing of study drug) should be completed before randomization.

Study drug will be titrated as tolerated to the maximum recommended dosage for optimal clinical effect over approximately 6 to 8 weeks, based on titration guidelines according to clinical response (see Section 6, Dosage and Administration). For all subjects, at any time, up-titration of open-label study drug may be slowed down if clinically indicated for tolerability, and may be accelerated if clinically indicated for seizure control.

Subjects will return for a clinic visit at Month 1 and Month 2 for dispensing of study medication.

Maintenance Period

Subjects should be maintained on the dosage achieved at the end of the titration period through the remainder of the open-label treatment phase, with the option for dosage adjustment as required for optimal clinical effect. Changes to this schedule will be based on a risk-benefit assessment of the subject's clinical condition by the investigator.

Clinic visits will be scheduled at Months 1, 2, 3, 6, 9, and 12/early withdrawal. Extra visits may be scheduled at the discretion of the investigator. Blood samples for PK evaluations will be taken at Months 1, 3, 6, and 12/early withdrawal.

Posttreatment Phase

[figure not shown]
Subjects will be contacted by telephone 30 days after the last dose of study drug to monitor adverse events and concomitant medications. Subjects who complete the study or discontinue early from the study may, at the discretion of the investigator, either continue on commercially available topiramate or levetiracetam or taper off topiramate or levetiracetam over a period of up to 2 weeks during the posttreatment phase.

Post-Study Follow-up Phase

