7.10. Clinical Laboratory Tests

Figures of the mean change from screening (+/- Standard Error) values in continuous hematology, urinalysis and serum chemistry laboratory parameters will be presented by visit. The observed and change from baseline values of lab parameters will also be summarized by visit. For calculation, the signs “<” or “>” will be removed and resulting numerical value will be used. The reference ranges for labs from the SAP will be used, not the reference ranges provided from the Covance.

The shift table of pre- vs. post-treatment with classes for below, within, and above normal ranges will be presented.

The number and percentage of subjects with markedly abnormal (low, high) laboratory hematology, urinalysis/24-hour urine and serum chemistry parameters during the study (from treatment start to 30 days after last dose or the end of treatment visit date, whichever is later) that were not present at baseline will be provided. [Appendix 2](#) presents the markedly abnormal criteria. The conversion factors for 25 Vitamin D, 1, 25 Vitamin D and PTH are also listed.

The laboratory data will be listed. The subjects with any laboratory results outside the reference ranges and the subjects with any markedly abnormal laboratory results will be listed.

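### SAP 7.9 imputes partial adverse-event onset dates to the first of the month or to January with no floor at first dose, so some early on-treatment events leave the treatment-emergent tables

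*SAP*

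**What the plan says.** SAP 7.9 defines treatment-emergent AEs (TEAEs) as those "which start or worsen after receipt of the first study drug and before the end of the REACH". The same paragraph gives the rule for incomplete onset dates: "AE's with partial onset date will be handled as follows: a missing day should be set to first of month". It continues: "If month is missing the missing month should be set to January". There is no exception for the month or year of first dose, and the AE stop date is not used. SAP 5.6 applies the same rule to medication dates.

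The TEAE flag feeds the incidence tables: overall, serious, leading to discontinuation, by severity, by relationship and of special interest. A listing of AEs is also planned, with no stated restriction to TEAEs.

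Protocol 11.4 says that the analysis includes every reported AE that begins in the treatment phase. Protocol 12.1.1 collects AEs from consent, and screening may last up to 35 days (Protocol 9.1.2), so there is a real pre-dose period for the flag to separate.

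At the other end, SAP 7.9 counts "AEs with onset date within therapeutic reach (i.e. 3 days") after the end of treatment, and serious AEs and deaths for 30 days. It does not define the end of treatment.

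**The concern.** Setting a missing day to the 1st, or a missing month to January, can only move an onset date earlier. Around first dose, that turns on-treatment events into pre-dose ones. The clause on worsening does not rescue an event that is new on treatment, because there is nothing earlier for it to have worsened from. The table then omits an event that Protocol 11.4 says belongs in it.

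The exposed period is the start of treatment, when titration takes place and when the protocol expects some of the risks of interest. The Introduction describes the vision symptoms as having "acute onset (within 1 month of initiating topiramate therapy"), and says that metabolic acidosis generally appears early. Partial dates are plausible, since parents report the AEs (Protocol 9.3) and visits after Month 3 are about 90 days apart.

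**Working it through.** The documents give no figure on this point to reproduce. The check applies the SAP rule literally and counts how often an on-treatment onset is moved to before first dose.

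**Example.** First dose on 15 March; an AE begins after dosing and is recorded only as March. The imputed onset is 1 March, which is before 15 March, so it is not a TEAE. If only the year is known, the imputed onset is 1 January, with the same result.

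**Inputs.** The imputation rule and TEAE definition are from SAP 7.9. Treatment length is 360 days (Time and Events Schedule). Two assumptions are not in the documents: first-dose dates are evenly spread, and onsets follow the patterns stated below.

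**Missing day, first 30 days.** Take a 30-day month, start day d = 1 to 30, and onset k = 0 to 29 days after dose. Onset falls in the same month if d + k ≤ 30, which gives 31 − d onset days. A start on the 1st loses nothing. The sum over d = 2 to 30 is 29 + 28 + … + 1 = 435, and 435 / (30 × 30) = 48.3%.

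**Missing day, 360 days.** The mean number of exposed days is 435 / 30 = 14.5, and 14.5 / 360 = 4.0%.

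**Missing month, 360 days.** Take start day d = 1 to 365 of the year. The number of the 360 onset days in the same calendar year is min(360, 366 − d), and a start on 1 January loses nothing. Days d = 2 to 6 give 5 × 360 = 1,800. Days d = 7 to 365 give 359 + 358 + … + 1 = 64,620. The share is 66,420 / (365 × 360) = 50.5%.

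**Calendar check.** The rule was also run over every start date in a three-year span, with onset counted from the day after first dose:

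| Onset pattern | Day missing | Month missing |
|---|---|---|
| Even over first 30 days | 45.9% | 95.5% |
| Even over first 56 days | 24.6% | 91.9% |
| Half in first 56 days, rest even to day 360 | 12.3% | 67.3% |
| Even over 360 days | 3.8% | 50.3% |

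The small differences from the hand figures come from real month lengths and from leaving out the day of dosing. Protocol 6 puts the first dose in the evening of Day 1, so either convention for that day is defensible.

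A missing-day AE in the month of first dose is moved before first dose for 96.7% of start dates, that is, all except the 1st. Missing-day AEs in any later month are unaffected at this end, as are year-only AEs in the next calendar year.

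**Opposite error at the end.** Take a missing-day, non-serious AE that truly begins k = 4 to 30 days after treatment ends. With onset on day m of its month, the imputed date is m − 1 days earlier. It falls inside the 3-day limit if k − (m − 1) ≤ 3, so m ≥ k − 2. In a 30-day month the probability is (33 − k) / 30, and its average over k = 4 to 30 is 16 / 30 = 53%. The calendar run gave 54%. These events are wrongly counted as TEAEs.

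**The case against.** The strongest reply is that little depends on this. Growth, bone density and stone summaries do not use the TEAE flag, no formal testing is planned (SAP 7), and affected AEs stay in the listing. Bicarbonate is measured on dated samples and reported by visit and as marked abnormalities (SAP 7.10), so acidosis does not rest on AE dates alone. Regular visits, a take-home health record and data queries should make year-only dates uncommon, and serious AEs are reported within 24 hours (Protocol 12.3.2). All of this stands. It limits the consequence, but the rule still gives the wrong answer when it applies.

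Stronger readings that a reader might infer are not supported:

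- *TEAE incidence is biased downward overall.* The start-of-treatment error runs one way, but the end-of-treatment error runs the other, and the documents do not give the number of partial dates at either end.
- *The 3-day limit discards most of the taper.* Protocol 3.1 lets subjects "taper off topiramate or levetiracetam over a period of up to 2 weeks during the posttreatment phase". If treatment ends before the taper, 14 − 3 = 11 days of a full taper are outside the limit, for non-serious AEs only. But SAP 5.4 runs treatment to the last dose of topiramate or levetiracetam. If that includes taper doses, none of the taper is outside. The documents do not settle which applies.
- *The AE window should match the laboratory window.* SAP 7.10 counts laboratory flags "from treatment start to 30 days after last dose or the end of treatment visit date, whichever is later". That does not make 3 days wrong for AEs, because Protocol 11.4 confines the AE analysis to the treatment phase and the taper sits in the posttreatment phase.
- *Stones found at a late withdrawal visit are lost.* SAP 7.1 summarises stones from ultrasound findings, independently of the TEAE flag.

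**Conclusion.** The point holds for a defined set of events: new on-treatment AEs with a missing day in the calendar month of first dose, or a missing month in the calendar year of first dose. SAP 7.9 dates them before first dose and drops them from the TEAE tables, contrary to Protocol 11.4.

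The percentages in the working are shares of partially dated AEs, not of all AEs, and depend on the assumed start and onset patterns. The effect on actual counts, and its net direction, cannot be determined from the documents. This should be fixed, because the AE tables are core output of a safety trial and the correction is simple. It does not threaten the growth, bone or kidney-stone results.

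**What to change.** Add to SAP 7.9: where the known parts of the onset date match the month and year of first dose (or the year alone, when the month is missing), and the stop date is not before first dose, set onset to the first-dose date and count the AE as treatment-emergent. Otherwise keep the first-of-month and January rule. The loss at the start of treatment then falls to zero by construction, since no on-treatment AE can stop before first dose.

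Separately, state in SAP 7.9 whether the end of treatment, from which the 3 days are counted, means the last dose including taper doses, and reconcile this with SAP 5.4 and the protocol's posttreatment phase.

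The cost is a few sentences and a few lines of programming, with no new data. The downside is that a few screening-phase AEs with partial dates will count as treatment-emergent.
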